Appendix D Actions Required in Cases of Increases in Liver Biochemistry and Evaluation of Hy's Law

D 1 Introduction

This appendix describes the process to be followed to identify and appropriately report Potential Hy's Law (PHL) cases and of Hy's Law (HL) cases. It is not intended to be a comprehensive guide to the management of elevated liver biochemistries.

During the course of the study, the investigator will remain vigilant for increases in liver biochemistry. The investigator is responsible for determining whether a subject meets PHL criteria at any point during the study.

All sources of laboratory data are appropriate for the determination of PHL and HL events; this includes samples taken at scheduled study visits and other visits including central and all local laboratory evaluations even if collected outside of the study visits; for example, PHL criteria could be met by an elevated alanine aminotransferase (ALT) from a central laboratory **and/or** elevated total bilirubin (TBL) from a local laboratory.

The investigator will also review adverse event (AE) data (for example, for AEs that may indicate elevations in liver biochemistry for possible PHL events).

The investigator participates, together with MedImmune clinical project representatives, in review and assessment of cases meeting PHL criteria to agree whether HL criteria are met. Hy's Law criteria are met if there is no alternative explanation for the elevations in liver biochemistry other than drug-induced liver injury (DILI) caused by the investigational product.

The investigator is responsible for recording data pertaining to PHL/HL cases and for reporting AEs and SAEs according to the outcome of the review and assessment in line with standard safety reporting processes.

D 2 Definitions

D 2.1 Potential Hy's Law

Aspartate transaminase (AST) or ALT $\geq 3 \times$ upper limit of normal (ULN) **together with** TBL $\geq 2 \times$ ULN at any point during the study following the start of investigational product irrespective of an increase in alkaline phosphatase (ALP).

D 2.2 Hy's Law

AST or ALT $\geq 3 \times$ ULN **together with** TBL $\geq 2 \times$ ULN, where no other reason, other than the investigational product, can be found to explain the combination of increases; eg, elevated ALP indicating cholestasis, viral hepatitis, or another drug.

For potential Hy's Law and Hy's Law, the elevation in transaminases must precede or be coincident with (ie, on the same day) the elevation in TBL, but there is no specified timeframe within which the elevations in transaminases and TBL must occur.

D 3 Identification of Potential Hy's Law Cases

In order to identify cases of potential Hy's Law, it is important to perform a comprehensive review of laboratory data for any subject who meets any of the following identification criteria in isolation or in combination:

- $ALT \geq 3 \times ULN$
- $AST \geq 3 \times ULN$
- $TBL \geq 2 \times ULN$

The investigator will, without delay, review each new laboratory report and if the identification criteria are met will:

- Notify the sponsor study representative
- Determine whether the subject meets potential Hy's Law criteria (see Section [D 2](#)) by reviewing laboratory reports from all previous visits
- Promptly enter the laboratory data into the laboratory eCRF

D 4 Follow-up

D 4.1 Potential Hy's Law Criteria Not Met

If the subject does not meet potential Hy's Law criteria the investigator will:

- Inform the study representative that the subject has not met potential Hy's Law criteria.
- Perform follow-up on subsequent laboratory results according to the guidance provided in the study protocol.

D 4.2 Potential Hy's Law Criteria Met

If the subject does meet potential Hy's Law criteria the investigator will:

- Notify the sponsor study representative who will then inform the study team
- Within 1 day of PHL criteria being met, the investigator will report the case as an SAE of Potential Hy's Law; serious criteria 'Important medical event' and causality assessment 'yes/related' according to the Clinical Study Protocol process for SAE reporting.

- For subjects that met PHL criteria prior to starting investigational product, the investigator is not required to submit a PHL SAE unless there is a significant change in the subject's condition.

The medical monitor contacts the investigator, to provide guidance, discuss and agree an approach for the study subjects' follow-up and the continuous review of data. Subsequent to this contact the investigator will:

- Monitor the subject until liver biochemistry parameters and appropriate clinical symptoms and signs return to normal or baseline levels, or as long as medically indicated
- Investigate the etiology of the event and perform diagnostic investigations as discussed with the medical monitor.
- If at any time (in consultation with the medical monitor) the potential Hy's Law case meets serious criteria, report it as an SAE using standard reporting procedures

D 5 Review and Assessment of Potential Hy's Law Cases

The instructions in this section should be followed for all cases where potential Hy's Law criteria are met.

No later than 3 weeks after the biochemistry abnormality was initially detected, the medical monitor will contact the investigator in order to review available data and agree on whether there is an alternative explanation for meeting potential Hy's Law criteria other than DILI caused by the investigational product, to ensure timely analysis and reporting to health authorities within 15 calendar days from date PHL criteria were met. The medical monitor and Global Safety Physician will also be involved in this review together with other subject matter experts as appropriate.

According to the outcome of the review and assessment, the investigator will follow the instructions below.

If there is an agreed alternative explanation for the ALT or AST and TBL elevations, a determination of whether the alternative explanation is an AE will be made and subsequently whether the AE meets the criteria for a SAE:

- If the alternative explanation is **not** an AE, record the alternative explanation on the appropriate eCRF
- If the alternative explanation is an AE/SAE: update the previously submitted PHL SAE and AE CRFs accordingly with the new information (reassessing event term; causality and seriousness criteria) following the sponsor's standard processes

If it is agreed that there is **no** explanation that would explain the ALT or AST and TBL elevations other than the investigational product:

- Send updated SAE (report term ‘Hy’s Law’) according to sponsor standard processes
 - The ‘Medically Important’ serious criterion should be used if no other serious criteria apply
 - As there is no alternative explanation for the HL case, a causality assessment of ‘related’ should be assigned.

If, there is an unavoidable delay of over 15 calendar days in obtaining the information necessary to assess whether or not the case meets the criteria for Hy’s Law, then it is assumed that there is no alternative explanation until such time as an informed decision can be made:

- Provide any further update to the previously submitted SAE of PHL (report term now ‘Hy’s Law case’) ensuring causality assessment is related to investigational product and seriousness criteria is medically important, according to clinical study protocol (CSP) process for SAE reporting
- Continue follow-up and review according to agreed plan. Once the necessary supplementary information is obtained, repeat the review and assessment to determine whether HL criteria are still met. Update the previously submitted PHL SAE report following CSP process for SAE reporting, according to the outcome of the review and amending the reported term if an alternative explanation for the liver biochemistry elevations is determined.

D 6 Laboratory Tests

The list below represents the standard, comprehensive list of follow-up tests which are recommended when using a central laboratory. For individual studies, the list may be reduced to a subset of tests after consultation with the Hepatic Safety Knowledge Group.

Some of the tests may also be considered for use with local laboratories that have respective testing capabilities. Any test results need to be recorded in the CRF.

Hy’s Law Lab Kit for Central Laboratories

Additional standard chemistry and coagulation tests	GGT LDH Prothrombin time INR
Viral hepatitis	IgM anti-HAV IgM and IgG anti-HBc HBsAg HBV DNA IgM and IgG anti-HCV HCV RNA

	IgM anti-HEV HEV RNA
Other viral infections	IgM & IgG anti-CMV IgM & IgG anti-HSV IgM & IgG anti-EBV
Alcoholic hepatitis	Carbohydrate deficient transferrin (CD-transferrin)
Autoimmune hepatitis	Antinuclear antibody (ANA) Anti-Liver/Kidney Microsomal Ab (Anti-LKM) Anti-Smooth Muscle Ab (ASMA)
Metabolic diseases	alpha-1-antitrypsin Ceruloplasmin Iron Ferritin Transferrin Transferrin saturation

References

Aithal et al 2011, Clinical Pharmacology and Therapeutics 89(6):806-815.

Food and Drug Administration (FDA) Guidance for Industry (issued July 2009) ‘Drug-induced liver injury: Premarketing clinical evaluation’:

<http://www.fda.gov/downloads/Drugs/GuidanceComplianceRegulatoryInformation/Guidances/UCM174090.pdf>

Appendix E Genetic Research

Rationale and Objectives

MedImmune intends to collect and store DNA for genetic research to explore how genetic variations may affect clinical parameters, risk and prognosis of diseases, and the response to medications. Genetic research may lead to better understanding of diseases, better diagnosis of diseases or other improvements in health care and to the discovery of new diagnostics, treatments or medications.

In addition, collection of DNA samples from populations with well described clinical characteristics may lead to improvements in the design and interpretation of clinical trials and, possibly, to genetically guided treatment strategies.

Genetic Research Plan and Procedures

Selection of genetic research population

Study selection record

All subjects will be asked to participate in this genetic research. Participation is voluntary and if a subject declines to participate there will be no penalty or loss of benefit. The subject will not be excluded from any aspect of the main study.

Inclusion criteria

For inclusion in this genetic research, subjects must fulfill all inclusion criteria described in the main body of the Clinical Study Protocol **and**:

- Provide informed consent for the genetic sampling and analyses.

Exclusion criteria

Exclusion from this genetic research may be for any of the exclusion criteria specified in the main study

Discontinuation of subjects from this genetic research

Specific reasons for discontinuing a subject from this genetic research are:

Withdrawal of consent for genetic research: Subjects may withdraw from this genetic research at any time, independent of any decision concerning participation in other aspects of the main study. Voluntary discontinuation will not prejudice further treatment. Procedures for discontinuation are outlined in Section 4.1.8 of the protocol.

Collection of samples for genetic research

The blood sample for genetic research will be obtained from the subjects at Day -2. Although DNA is stable, early sample collection is preferred to avoid introducing bias through

excluding subjects who may withdraw due to an AE, such subjects would be important to include in any genetic analysis. If for any reason the sample is not drawn at Day -2, it may be taken at any visit until the last study visit. Only one sample should be collected per subject for genetics during the study. Samples will be collected, labelled, stored and shipped as detailed in the Laboratory Manual.

Coding and storage of DNA samples

The processes adopted for the coding and storage of samples for genetic analysis are important to maintain subject confidentiality. Samples will be stored for a maximum of 15 years, from the date of last subject last visit, after which they will be destroyed. DNA is a finite resource that is used up during analyses. Samples will be stored and used until no further analyses are possible or the maximum storage time has been reached.

An additional second code will be assigned to the blood either before or at the time of DNA extraction replacing the information on the sample tube. Thereafter, the sample will be identifiable by the second, unique number only. This number is used to identify the sample and corresponding data at the MedImmune genetics laboratories, or at the designated organization. No personal details identifying the individual will be available to any person (MedImmune employee or designated organizations working with the DNA).

The link between the subject enrollment/randomization code and the second number will be maintained and stored in a secure environment, with restricted access at MedImmune or designated organizations. The link will be used to identify the relevant DNA samples for analysis, facilitate correlation of genotypic results with clinical data, allow regulatory audit and to trace samples for destruction in the case of withdrawal of consent.

Ethical and Regulatory Requirements

The principles for ethical and regulatory requirements for the study, including this genetics research component, are outlined in Section 7 of the protocol.

Informed consent

The genetic component of this study is optional and the subject may participate in other components of the main study without participating in the genetic component. To participate in the genetic component of the study the subject must sign and date both the consent form for the main study and the genetic component of the study. Copies of both signed and dated consent forms must be given to the subject and the original filed at the study center. The principal investigator(s) is responsible for ensuring that consent is given freely and that the subject understands that they may freely discontinue from the genetic aspect of the study at any time.

Subject data protection

MedImmune will not provide individual genotype results to subjects, any insurance company, any employer, their family members, general physician unless required to do so by law.

Extra precautions are taken to preserve confidentiality and prevent genetic data being linked to the identity of the subject. In exceptional circumstances, however, certain individuals might see both the genetic data and the personal identifiers of a subject. For example, in the case of a medical emergency, a MedImmune physician or an investigator might know a subject's identity and also have access to his or her genetic data. Also, regulatory authorities may require access to the relevant files, though the subject's medical information and the genetic files would remain physically separate.

Data management

Any genotype data generated in this study will be stored at a secure system at MedImmune and/or designated organizations to analyze the samples.

The results from this genetic research may be reported in a separate report from the CSR or published in scientific journals.

MedImmune and its designated organizations may share summary results (such as genetic differences from groups of individuals with a disease) from this genetic research with other researchers, such as Hospitals, Academic Organization or Health Insurance Companies. This can be done by placing the results in scientific databases, where they can be combined with the results of similar studies to learn even more about health and disease. The researchers can only use this information for health-related research purposes. Researchers may see summary results but they will not be able to see individual subject data or any personal identifiers.

Some or all of the clinical datasets from the main study may be merged with the genetic data in a suitable secure environment separate from the clinical database.

Statistical Methods and Determination of Sample Size

The number of subjects that will agree to participate in the genetic research is unknown. It is therefore not possible to establish whether sufficient data will be collected to allow a formal statistical evaluation or whether only descriptive statistics will be generated. A Statistical Analysis Plan will be prepared where appropriate.

SIGNATURE PAGE

This is a representation of an electronic record that was signed electronically and this page is the manifestation of the electronic signature

Document Name: d5670c00030-amendment-3		
Document Title:	d5670c00030-amendment-3	
		
Version Label:	2.0 CURRENT LATEST APPROVED	
Server Date (dd-MMM-yyyy HH:mm 'UTC'Z)		
		
		
		
		
		

SIGNATURE PAGE

This is a representation of an electronic record that was signed electronically and this page is the manifestation of the electronic signature

Document Name: d5670c00030-csp-amendment-3-redacted		
Document Title:	D5670C00030 Clinical Study Protocol amendment 3 Redacted	
Document ID:	Doc ID-004284523	
Version Label:	1.0 CURRENT LATEST APPROVED	
Server Date (dd-MMM-yyyy HH:mm 'UTC'Z)	Signed by	Meaning of Signature
07-May-2020 21:36 UTC	[name]	Content Approval

Notes: (1) Document details as stored in ANGEL, an AstraZeneca document management system.

| BMI | body mass index |
| CI | confidence interval |
| | |
| C_{max} | maximum-observed plasma drug concentration |
| C_{trough} | trough concentrations from the pre-dose plasma concentration data |
| C_{τ} | trough concentrations (C_{trough}) from the pre-dose plasma drug concentration data |
| CV | coefficient of variation |
| DEC | dose escalation committee |
| ECG | electrocardiogram |
| GLP-1 | glucagon-like peptide 1 |
| HbA1c | hemoglobin A1c |
| HCTD | highest clinically tolerated dose |
| ITT | Intent-to-Treat |
| PK | pharmacokinetics |
| PR | ECG PR interval |
| PT | MedDRA preferred term or WHO-DDE preferred term |
| QRS | ECG QRS interval |
| QT | ECG QT interval |
| QTc | ECG QT interval corrected for heart rate |
| QTcF | ECG QT interval corrected for heart rate using Fridericia's formula |
| RR | ECG RR interval |
| SAE | serious adverse event |
| SD | standard deviation |
| SOC | MedDRA system organ class |
| SPP | statistical programming plan |
| $t_{1/2}$ | apparent terminal elimination half-life |
| T2DM | type 2 diabetes mellitus |
| TEAE | treatment-emergent adverse event |
| WHO-DDE | World Health Organization drug dictionary enhanced |

1 INTRODUCTION

This document describes the statistical analysis methodology for protocol D5670C00030, a randomized, blinded, placebo-controlled study designed to evaluate the safety, tolerability, pharmacokinetics (PK), and efficacy of ascending doses of MEDI0382 in overweight or obese subjects with type 2 diabetes mellitus (T2DM). This document details the statistical summaries relating to each study objective and describes the general conventions and definitions that will be used. In addition, a set of table templates and specifications will be included in a statistical programming plan (SPP) to complement this document.

2 STUDY OVERVIEW

2.1 Study Objectives

2.1.1 Primary Study Objective(s)

Assess the safety and tolerability of MEDI0382 titrated up to a dose of [REDACTED] or to the highest clinically tolerated dose (HCTD) from a starting dose of [REDACTED]

2.1.2 Secondary Study Objectives

- To characterize the PK profile of MEDI0382 titrated up to a dose of [REDACTED] or to the highest clinically tolerated dose (HCTD)
- To characterize the immunogenicity of MEDI0382 titrated up to a dose of [REDACTED] or to the HCTD
- To assess the effects of MEDI0382, titrated up to a dose of [REDACTED] or to the HCTD, [REDACTED]
[REDACTED]
- To assess the effects of MEDI0382, titrated up to a dose of [REDACTED] or to the HCTD, on additional measures of glucose control
- To assess the effects of MEDI0382, titrated up to a dose of [REDACTED] or to the HCTD, on body weight

[REDACTED]

[REDACTED]

[REDACTED]

2.2 Study Design

[figure not shown]
This is a randomized, blinded, placebo-controlled study designed to evaluate the safety, tolerability, PK and efficacy of ascending doses of MEDI0382 in overweight or obese subjects with T2DM. This study will enroll subjects aged 18 to 74 years with a body mass index (BMI) 27 to 35 kg/m². Subjects will have a diagnosis of T2DM and inadequate blood glucose control as defined by a hemoglobin A1c (HbA1c) of 6.5% to 8.5% and will be on metformin monotherapy.

Twenty subjects will be enrolled to 2 cohorts: Cohort 1 (n = 8) and Cohort 2 (n = 12). For each cohort, subjects will be randomly assigned in a 3:1 ratio to receive MEDI0382 at doses titrated  or placebo. The study has a run-in period of 10 days and an up to 8-week up-titration treatment period (for the primary analysis) followed by a 3-week treatment extension period at the HCTD followed by a 28-day follow-up period.

In Cohort 1, MEDI0382 or matched placebo will be administered daily starting at  with the dose up-titrated weekly to , or until the HCTD is established (whichever occurs first). The dose escalation committee (DEC) will review 72-hour safety data when subjects reach the  dose levels to determine if the HCTD is established as these doses have not been previously studied in T2DM subjects and the safety profile is unknown. If the DEC determines that the current dose level is not being tolerated and does not approve progression to the next dose level, the preceding one will be declared as the HCTD.

Subjects in Cohort 2 will follow the up-titration schedule defined by Cohort 1, with the 3-week treatment extension period being conducted at the HCTD; thus, the duration of Cohort 2 subjects' participation in the study will be determined by the results obtained from Cohort 1. Dosing in Cohort 2 will occur ≥ 7 days after initiation of Cohort 1 ([Figure 2.2-1](#)).

Figure 2.2-1 Study Flow Diagram

2.3 Treatment Assignment and Blinding

Subjects will be randomized using a 3:1 ratio to receive either MEDI0382 or placebo via manual randomization.

This is a blinded study in which the subjects and investigator and staff performing evaluations are blinded to the identity of investigational product, while MedImmune staff involved in the study are unblinded. Investigational product and placebo are indistinguishable in appearance, identically labelled, and supplied as fully blinded kits.

2.4 Sample Size

The total study sample size is 20 subjects, who will be randomized by 2 cohorts: 8 subjects in Cohort 1 and 12 subjects in Cohort 2. For each cohort, subjects will be randomized in a 3:1 ratio to the MEDI0382 arm or the placebo arm. The sample size for this study was empirically determined to obtain adequate safety and tolerability evaluation. [REDACTED]

[REDACTED]

3 STATISTICAL METHODS

3.1 General Considerations

Data will be presented in data listings sorted by treatment, dose, subject number, and date collected, where appropriate. Tabular summaries will be presented by treatment arm. Categorical data will be summarized by the number and percentage of subjects in each category. Continuous variables will be summarized with descriptive statistics (eg, n, mean, median, SD, minimum, and maximum).

Analyses will be conducted for each cohort and for the two cohorts combined. Formal statistical modeling analysis for the secondary efficacy endpoints will be conducted for the two-cohort combined analyses. In general, unless stated otherwise, baseline will be defined as the last value prior to dosing.

Two analyses are planned for this study as follows:

- 1 A primary analysis after the up-titration period for Cohort 2, and
- 2 A final analysis after the safety follow-up period for Cohort 2.

Data analyses will be conducted using the SAS[®] System Version 9.4 or higher (SAS Institute Inc., Cary, NC) in a UNIX platform.

3.2 Analysis Populations

The analysis populations are defined in [Table 3.2-1](#).

Table 3.2-1 Analysis Populations

| Population | Description |
|----------------------------------|--|
| As-treated population | Subjects who receive any study investigational product will be included in the As-treated population and subjects will be analyzed according to the treatment they actually receive. |
| Intent-to-treat population (ITT) | Subjects who receive any study investigational product will be included in the ITT population and subjects will be analyzed according to the treatment they were randomized |

Table 3.2-1 Analysis Populations

| Population | Description |
|---------------------------|---|
| PK population | Subjects who have at least one measurable concentration time point of MEDI0382 |
| Immunogenicity Population | Subjects in the As-treated population who have at least one serum sample for immunogenicity testing |

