4.1.5 Withdrawal from the Study

Subjects are free to withdraw their consent to participate in the study (investigational product and protocol-defined assessments) at any time, without prejudice to further treatment. Subjects who withdraw consent will be asked about the reason(s) and the presence of any AEs. If the

subject is willing, the subject will be seen and assessed by the investigator (early discontinuation visit). AEs will be followed up, and all study medications should be returned by the subject. If a subject withdraws from further participation in the study, then no further study visits or data collection should take place.

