3.6 Immunogenicity

Analysis of immunogenicity will be based on the Immunogenicity population. The incidence and impact of anti-drug antibody (ADA) to MEDI0382 will be evaluated. The number and percentage of subjects with confirmed positive serum antibodies to MEDI0382 will be

reported by treatment. Titer data and cross-reactivity to glucagon-like peptide 1 (GLP-1) and glucagon (if applicable) will be listed.

The following categories will be utilized to describe the ADA response:

- ADA prevalence: subjects who are ADA positive at any visit (including baseline)
- Subjects who are ADA positive at baseline only
- Subjects who are ADA positive at baseline and positive post baseline
- Subjects who are ADA positive post-baseline only (treatment-induced ADA)
- Proportion of subjects who are treatment-boostered ADA; treatment-boostered ADA is defined as baseline ADA titer that was boosted to a 4-fold or higher level following drug administration
- ADA incidence (treatment-emergent ADA), defined as the sum of treatment-induced ADA (post-baseline positive only) and treatment-boostered ADA

A similar summary will be performed for ADA cross-reactivity to GLP-1 and/or glucagon (as data allows and if applicable).

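### ADA incidence needs a baseline and a post-baseline result, but its denominator needs only one sample at any time, so it can be misstated in either direction

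*SAP*

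**What the plan says.** SAP 3.2 (Table 3.2-1) admits to the Immunogenicity population "Subjects in the As-treated population who have at least one serum sample for immunogenicity testing". It does not say when the sample must have been taken. SAP 3.6 then states: "Analysis of immunogenicity will be based on the Immunogenicity population". It gives no other denominator.

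The categories in SAP 3.6 differ in what they need:

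- Prevalence counts a positive at any visit, so one sample is enough to contribute.
- The treatment-induced category is "Subjects who are ADA positive post-baseline only (treatment-induced ADA"), which presupposes a baseline result to compare with.
- The treatment-boosted category requires a "baseline ADA titer that was boosted to a 4-fold or higher level following drug administration", which needs two titers.
- The headline measure is "ADA incidence (treatment-emergent ADA), defined as the sum of treatment-induced ADA (post-baseline positive only) and treatment-boostered ADA".

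SAP 3.6 has no rule for a missing baseline or post-baseline sample and no not-evaluable category. The carry-forward rule in SAP 3.4.2.2 covers secondary efficacy only, and the no-imputation rule in SAP 3.7 covers PK parameters only.

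ADA from baseline to the end of the study is a secondary endpoint (Protocol 2.1.1, Table 2), and a predictable immunogenic profile is part of a secondary hypothesis (Protocol 1.7.2).

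**The concern.** The numerator of ADA incidence can contain only subjects with a post-baseline result, while the denominator can contain subjects without one. Read literally, the SAP 3.6 categories also mislabel subjects whose samples are incomplete:

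- **Negative at baseline, nothing later:** counted as not treatment-emergent, although no post-dose sample was tested.
- **Positive at baseline, nothing later:** placed with subjects positive at baseline only. The label is the same as for someone retested and found negative, so it reads as loss of antibody.
- **No baseline result, positive later:** can be placed with subjects positive post-baseline only and called treatment-induced, although the antibody may have been there before dosing.

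The first two cases pull the reported incidence down and the third pushes it up. With 15 subjects on MEDI0382, and results also shown by cohort, one misplaced subject is visible in the percentage.

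**Working it through.** **Inputs.** SAP 2.4 gives 20 subjects, 8 in Cohort 1 and 12 in Cohort 2, and says "For each cohort, subjects will be randomized in a 3:1 ratio to the MEDI0382 arm or the placebo arm". That gives 6:2 and 9:3, so 15 on MEDI0382 and 5 on placebo. The documents state no ADA rate, dropout rate or evaluable number, so there is no plan figure to reproduce. Two quantities are assumed: *m*, the MEDI0382 subjects with only a baseline sample (0 to 3), and *x*, the subjects with treatment-emergent ADA (1, 3 or 6).

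**Formula, baseline sample only.** Reported incidence is x/N. Incidence among subjects with a post-baseline result is x/(N − m). Their ratio is (N − m)/N, so the relative shortfall is m/N whatever x is. With N = 15 it is 1/15 = 6.7%, 2/15 = 13.3% and 3/15 = 20.0% for m = 1, 2 and 3.

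| x | Reported x/15 | m = 1: x/14 | m = 2: x/13 | m = 3: x/12 |
|---|---|---|---|---|
| 1 | 6.7% | 7.1% | 7.7% | 8.3% |
| 3 | 20.0% | 21.4% | 23.1% | 25.0% |
| 6 | 40.0% | 42.9% | 46.2% | 50.0% |

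The smallest shortfall for m of at least 1 is 1/14 − 1/15 = 0.5 points. The largest is 6/12 − 6/15 = 10.0 points. With m = 0 there is none.

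**By cohort, x = 2 assumed.** Cohort 1 (6 active): 2/6 = 33.3% reported, against 2/5 = 40.0% at m = 1. Cohort 2 (9 active): 2/9 = 22.2%, against 2/8 = 25.0%.

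**Opposite direction.** Suppose 3 subjects are truly treatment-emergent, one other has only a baseline sample, and one more has no baseline result but a pre-existing antibody found later and called induced. The reported figure is 4/15 = 26.7%. Among the 13 subjects with both results it is 3/13 = 23.1%. The net error is now an overstatement.

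**How such cases could arise.** Protocol 4.1.6 keeps subjects who stop the product in follow-up, including the visit 28 days after the last dose. Table 7 schedules an ADA sample at that visit, which also serves as the early discontinuation visit. Protocol 4.1.6 lists the exceptions: withdrawal of consent, loss to follow-up, starting another treatment and entering another study. Under Protocol 4.1.5 a subject who withdraws consent attends the early discontinuation visit only if willing; for anyone who withdraws from further participation, "then no further study visits or data collection should take place". Cases with only a baseline sample should therefore be confined mainly to those exceptions and to refusal of that visit. The up-titration sampling times (Table 6) are not visible in the public text, so their number cannot be estimated.

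**The case against.** A reader might infer that ADA incidence will be understated, and more so on MEDI0382, because gastrointestinal events will drive early withdrawals. The documents do not support this, for three reasons. Nothing shows that subjects with only a baseline sample will occur. Stopping the product for an adverse event is not leaving the study, because Protocol 4.1.6 keeps that subject in follow-up with a scheduled ADA sample, and no dropout rate by arm is given. A missing baseline can push the figure the other way. Any ADA samples in Table 6 would shrink the problem further.

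The case for leaving the plan alone adds that immunogenicity is descriptive, with no test, power or decision attached, and that the differences are small against the precision available. Exact 95% intervals are 4.3% to 48.1% for 3/15 and 5.0% to 53.8% for 3/13. In a trial of 20, the listings would help a careful reader find the affected subjects, and the table templates in the statistical programming plan, which is not available here, may show the n used. Nor is the restricted rate necessarily the true one: early leavers have the least exposure, so dropping them could itself raise the rate.

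All of this stands as a limit on size and certainty. It does not remove the mismatch. The SAP states one denominator, that denominator admits subjects who cannot be classified, and no rule says what to do with them.

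**Conclusion.** The point holds as a correction to a stated denominator. The Immunogenicity population suits prevalence but not the categories that compare baseline with later results. The relative shortfall of 1/15 per MEDI0382 subject with only a baseline sample follows from the allocation. The range of 0.5 to 10 percentage points rests on assumed values of m from 1 to 3 and x from 1 to 6. The direction is open once missing baselines are allowed for, and the effect is nil if every subject has both results. It is a minor matter: no test or sample size depends on it. It is still worth settling, because the rule as written can report an unmeasured outcome as a negative one.

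**What to change.** In SAP 3.6, with a matching line in Table 3.2-1:

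- Keep the present Immunogenicity population for overall ADA prevalence.
- For positive at baseline only, positive at baseline and post-baseline, treatment-induced, treatment-boosted and ADA incidence, use as denominator the subjects with a baseline result and at least one post-baseline ADA result. A subject with no baseline result but a later positive then counts towards prevalence and is not evaluable for incidence.
- Show that n, and the number not evaluable, in each column.
- Summarise GLP-1 and glucagon cross-reactivity among the ADA-positive subjects actually tested, with that n shown. Protocol 4.3.5 makes this testing optional and limits it to confirmed-positive samples, so the baseline-plus-post-baseline denominator would again count untested subjects as negative.

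The cost is a few lines of SAP text and no new data. The downside is that denominators may be one or two subjects smaller.
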